### 9.10 Exclusion Criteria for Groups 1, 2, 3 (Year 2)

An individual will be excluded from participating in this trial if any one of the following criteria is fulfilled:

1. Pregnant, as determined by a positive urine or serum beta human chorionadotropin ( $\beta$ -hCG) test (*if female*).

NOTE: Pregnancy is also a criterion for discontinuation of any further vaccine dosing

2. Menstruating females 11 years of age and younger. (In order to avoid cultural implications of further assessing pregnancy potential i.e. sexual activity in this age group.)
3. Behavioral, cognitive, or psychiatric disease that in the opinion of the investigator affects the ability of the subject to understand and comply with the study protocol at a level appropriate for the subject's age.
4. Hemoglobin, white blood cell (WBC), absolute neutrophil count, or platelet levels outside the local laboratory-defined limits of normal. (Subjects may be included at the investigator's discretion for "not clinically significant" values outside of normal range and  $\leq$  Grade 2.)
5. Alanine transaminase (ALT) or creatinine (Cr) level above the local laboratory-defined upper limit of normal. (Subjects may be included at the investigator's discretion for "not clinically significant" values outside of normal range and  $\leq$  Grade 2.)
6. Infected with HIV
7. Evidence of clinically significant neurologic, cardiac, pulmonary, hepatic, endocrine, rheumatologic, autoimmune, hematological, oncologic, or renal disease by history, physical examination, and/or laboratory studies including urinalysis.
8. History of receiving any investigational product within the past 30 days.
9. Medical, occupational, or family problems as a result of alcohol or illicit drug use during the past 12 months.
10. History of a severe allergic reaction or anaphylaxis.
11. Known:
  - Severe asthma, defined as asthma that is unstable or required emergent care, urgent care, hospitalization, or intubation during the past 2 years, or that has required the use of oral or parenteral corticosteroids at any time during the past 2 years.
  - Autoimmune or antibody-mediated disease including but not limited to: systemic lupus erythematosus, rheumatoid arthritis, multiple sclerosis, Sjögren's syndrome, or autoimmune thrombocytopenia.
  - Immunodeficiency syndrome.
  - Seizure disorder (exception: history of simple febrile seizures)
  - Asplenia or functional asplenia.
  - Use of chronic ( $\geq 14$  days) oral or intravenous (IV) corticosteroids (excluding topical or nasal) at immunosuppressive doses (i.e., prednisone  $> 10$  mg/day) or immunosuppressive drugs within 30 days of Study Day 0.

- Allergy to latex or neomycin
  - Adverse reaction to hepatitis A and/or typhoid and/or meningococcal vaccine in the past
  - Adverse reaction to artemether/lumefantrine in the past
12. Receipt of:
- Live vaccine within the past 4 weeks or a killed vaccine within the past 2 weeks to enrollment.
  - Immunoglobulins and/or blood products within the past 6 months.
13. Any other condition that in the opinion of the investigator would jeopardize the safety or rights of a subject participating in the trial, interfere with the evaluation of the study objectives, or would render the subject unable to comply with the protocol.

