- Successfully rescreen and meet inclusion/exclusion criteria for Year 2
- Receive either AL (1-8 years old only) and/or vaccine (scheduled dose #4)

**Screen Failures:** Subjects are considered screen failures when they meet 1 of the following criteria after signing consent:

- Screening results reveal that the subject is ineligible per **Section 11.1**
- Subject withdraws consent before being randomized.
- Family compound/Vaccine unit preliminary enrollment is significantly lower than approximately 80%, including low estimated pediatric participation.

**Discontinued:** Subjects are considered discontinued when they meet 1 or more of the following criteria:

- Subject withdraws consent after being vaccinated and/or randomized.
- Subject is withdrawn by the PI/sponsor after being vaccinated and/or randomized.

**Completed:** Subjects are considered completed when they complete the final study visit for their arm.

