#### **9.6 Inclusion Criteria for Groups 1, 2, 3, (Year 2)**

All of the following criteria must be fulfilled for a volunteer to continue to participate in this trial:

1. Previously enrolled in the study and has received at least 1 vaccination.
2. Available for the duration of the trial.
3. In good general health and without clinically significant medical history in the opinion of the investigator.
4. Females of childbearing potential must be willing to use reliable contraception from 21 days prior to scheduled vaccine dose #4 and until 1 month after the 4th vaccination.
  - A reliable method of birth control includes **one** of the following:
    1. Confirmed pharmacologic contraceptives (parenteral) delivery;
    2. Intrauterine or implantable device

EXCEPTIONS to required pregnancy prevention includes the following:

1. Postmenopausal state: defined as no menses for 12 months without an alternative medical cause
2. Surgical sterilization
3. Unmarried AND not sexually active AND menstruating OR not menstruating females 12-17 years of age

4. NOTE: if a female of childbearing potential's status changes during the course of vaccination through 1 month post vaccination (e.g. they become  $\geq 18$  years of age, married, or sexually active), the female will be required to start reliable contraception
5. Willing to have blood samples stored for future research.

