#### 10.6 Prohibited Medications and Procedures

Treatment with any of the following medications/procedures could potentially interfere with vaccine-induced immunity and will not be permitted. Use of any of these during the study may exclude a subject from receiving further doses of the study vaccine. However, the subject will be encouraged to remain in the study for safety evaluations.

- Licensed killed vaccines in the 2-week period prior to and following each vaccination or licensed live vaccines in the 4-week period prior to and following each vaccination.
- Receipt of immunoglobulins or any blood products up to 6 months prior to the first study vaccination and continuing for 30 days after administration of the last vaccination.

- Chronic oral or IV administration ( $\geq 30$  days) of immunosuppressive doses of steroids (i.e., prednisone  $> 10$  mg per day), immunosuppressants, or other immune-modifying drugs from each day of vaccination to 2 weeks following each vaccination.
- Any investigational drug or investigational vaccine other than the study vaccine during the study period.
- Required surgical removal of the spleen or the development of a hematologic or other disease that would interfere with normal immunity.

Over-the-counter medications such as acetaminophen or ibuprofen may be used to help relieve symptoms from vaccination and are not considered prohibited.

Use of antimalarial medications or antibiotics that have antimalarial activity during the study period is not exclusionary but will be documented by clinical staff.

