NOTE: if a female of childbearing potential's status changes during the course of vaccination through 1 month post vaccination (e.g. they become  $\geq 18$  years of age, married, or sexually active), the female will be required to start reliable contraception

- Administer a complete physical examination, including vital signs (blood pressure, temperature, and heart rate), height/length, and weight. (Year 1 + 2)
- HIV pre- and post-test counseling as indicated including follow-up contact with subject to report the results and referral for appropriate medical care if indicated. (Year 1 + 2)
- Obtain blood for complete blood count with differential (CBC w/diff) and platelet count, ALT, Cr, and HIV antibody. (Year 1 + 2)
- Obtain urine for urinalysis/urine dipstick for protein and blood and, for females of childbearing potential, obtain urine (or serum) for pregnancy testing. (UA, Year 1 only; Pregnancy testing Year 1 + 2)

- Pregnancy testing (urine or serum) will be completed on all females 9 years of age and older as indicated in **Appendix A**.
- Obtain a 12-lead electrocardiogram (EKG). (Year 1 only)

If screening laboratories are completed within  $\leq 2$  days prior to Study Day -7 prior to vaccination (AL dosing), these clinical laboratory values (CBC w/diff, ALT, Cr) may be used for Study Day -7 assessments and do not need to be repeated.

If initial screening is completed  $>56$  days prior to Study Day 0 (day of vaccination #1), the following screening procedures (per procedure; only those  $>56$  days prior to Study Day 0) will need to be repeated: repeat a new Malaria Comprehension Exam, updated medical history, repeat screening labs (except HIV unless determined change in risk), repeat physical exam, and repeat EKG. Subjects will then be reassessed for eligibility based on the re-screening information.

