**Study Day 448 (PILOT) + 392 (MAIN) ( $\pm$ 112 days; day of Vaccination #4)**

The following evaluations/procedures will be completed before vaccination:

1. Perform interim history and physical examination, focusing on any acute complaints.
2. Record vital signs (blood pressure, temperature, and heart rate).
3. During the physical examination, study staff will educate the subject regarding signs and symptoms of potential adverse events (AEs) and indications for use of antipyretics if fever, headache, or malaise occurs.
4. For females, obtain a urine or serum sample for  $\beta$ -hCG testing. Ensure that the test is negative before vaccinating.
5. For females, ensure agreement and compliance with pregnancy prevention before vaccinating.
6. Obtain approximately 11 mL of blood for CBC with differential and platelet count, ALT, creatinine, malaria blood smear, malaria PCR, anti-Pfs230 antibody ELISA, and standard membrane feeding assay (SMFA).
7. Confirm continued eligibility to receive vaccination.
8. Administer the vaccine.

The following evaluations/procedures will be completed following vaccination:

1. Observe the subject for at least 30 minutes after vaccination to evaluate immediate adverse reactions.
2. Record vital signs (blood pressure, temperature, and heart rate).
3. Perform interim history and physical examination, focusing on any acute complaints.
4. Record AEs and concomitant medications, if applicable.

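### The Year 2 immunosuppression exclusion (9.10 item 11) is still tied to vaccination #1, so it does not screen the 30 days before dose 4

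*Combined protocol and SAP*

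**What the plan says.** Section 8.4 makes the Year 2 criteria a condition of continuing: to be re-enrolled, a participant must "Successfully rescreen and meet inclusion/exclusion criteria for Year 2". For Groups 1 to 3 the exclusions are in 9.10. Its item 11 covers chronic oral or IV steroids (14 days or more, at immunosuppressive doses) "or immunosuppressive drugs within 30 days of Study Day 0". The Year 1 list, 9.8 item 13, has the same wording.

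Section 11.1.1 fixes the anchor when it refers to "Study Day 0 (day of vaccination #1), the following screening procedures". Appendix B labels the vaccination #1 visit the same way. Study days then keep counting: section 7.1 and Appendix B put dose 4 at Day 392 (main) and Day 448 (pilot).

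The on-study medication rule in 10.6 covers treatments that "could potentially interfere with vaccine-induced immunity and will not be permitted". For this class it names chronic steroids (30 days or more), "immunosuppressants, or other immune-modifying drugs from each day of vaccination to 2 weeks following each vaccination".

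**The concern.** A 30-day immunosuppression rule in a Year 2 eligibility list makes sense only if it protects the Year 2 dose. As worded, it re-tests a period around the first dose, more than a year before the nominal date of dose 4. Under 9.6 item 1, anyone entering Year 2 must be "Previously enrolled in the study and has received at least 1 vaccination", so each of them has already faced the identical Year 1 rule. The bullet therefore adds almost nothing.

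What is at stake is a defined window before dose 4 for drugs that the protocol itself says could interfere with the immune response. Section 17.3.2.1 intends to combine Year 1 and Year 2 endpoints for vaccine activity, so the response to dose 4 counts. A site applying the bullet literally would find no exclusion under it for a participant whom the Year 1 rule would have excluded before dose 1.

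**Working it through.** The plan gives no figure to reproduce. The check compares day intervals and then looks for another rule that covers the same period.

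**Inputs.** The rule has a 30-day window anchored at Day 0 (9.10 item 11; 11.1.1). Nominal dose 4 is Day 392 main and Day 448 pilot (7.1). The Appendix A visit window for dose 4 is ±112 days, counted from the preceding vaccination.

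**Step 1: days the rule covers.** Read two-sided, which is its widest sense: 0 - 30 = -30 to 0 + 30 = 30.

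**Step 2: days that need covering** (dose 4 minus 30, up to dose 4), and the separation from Day 30.

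| Phase | Look-back needed | Rule covers, at most | Overlap | Separation |
|---|---|---|---|---|
| Main | 392 - 30 = 362, to 392 | -30 to 30 | 0 days | 362 - 30 = 332 days |
| Pilot | 448 - 30 = 418, to 448 | -30 to 30 | 0 days | 418 - 30 = 388 days |

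**Step 3: does the visit window change this?** I give no exact range for dose 4, because its timing runs from the actual date of the preceding dose and vaccination #3 has its own ±56-day window. The pilot labels also disagree. Day 448 is 448 - 126 = 322 days after nominal dose 3, but Appendix A marks that visit as 336; the main arms agree at 392 - 56 = 336. A bound is enough. No preceding dose falls before Day 0, so with the 336-day interval dose 4 is no earlier than Day 336 - 112 = 224, and the look-back starts no earlier than 224 - 30 = Day 194. With 322 the figures are 210 and 180. Both are later than Day 30, so the overlap is still zero.

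**Step 4: is there another defined look-back?**

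- 10.6 restricts these drugs from the vaccination day to two weeks afterwards, with nothing before the dose. Its steroid threshold is 30 days or more, against 14 or more in 9.10.
- 10.4 allows deferral for a prohibited medication but takes its definition from 10.6.
- 10.3 lists only hypersensitivity and a positive pregnancy test.

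**Step 5: who is left.** Disease-based rules remove many candidates: severe asthma, including steroid use in the past 2 years, and autoimmune disease (9.10 item 11); clinically significant disease (item 7); good general health (9.6 item 3); and, in 10.6, "the development of a hematologic or other disease that would interfere with normal immunity". Outside those, two kinds of participant meet no fixed exclusion:

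- those whose treatment ended in the 30 days before dose 4;
- those on a 14- to 29-day immunosuppressive steroid course at dose 4.

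**The case against.** The strongest reply is that this is a copied phrase whose intent is plain. The list is headed Year 2 and is applied at rescreening. The companion list, 9.6 item 4, already times contraception to dose 4. Appendix A shows the dose 4 visit as 336/0. Investigators can also exclude under 9.10 item 13 anyone whose condition would interfere with the study objectives, and they confirm eligibility on the day of dose 4. Doses 2 and 3 have no such look-back either.

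Much of this stands. The intent is recoverable, and discretion is real, so it would be too strong to say that the protocol forces a wrong eligibility decision. Three things do not stand:

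- The 336/0 entry is in the row counting days since vaccination. The study-day row in the same tables reads 392 or 448, so Study Day 0 is not redefined.
- Discretion does not replace a defined window that the protocol chose to include.
- Doses 2 and 3 have no such rule by design. Year 2 has one that cannot operate. The forward-only approach in 10.6 is not criticised here.

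A reader might also infer that Year 2 immunogenicity or vaccine activity results are biased. The documents do not support that. They give no count of such courses, the wording applies to both arms, the primary analysis follows intention to treat (17.3.2.3), and concomitant medications are recorded (10.5), so affected participants could be identified.

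**Conclusion.** The point holds as a minor error in an operative eligibility rule. Read literally, 9.10 item 11 screens none of the 30 days before dose 4 in either phase, and no other defined rule does. The participants in the two groups identified above can be excluded only by investigator judgement (9.10 item 13, 10.4). Their number is unknown. The separations of 332 and 388 days show only that the windows do not meet; they do not measure harm.

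This rests on three readings: that Study Day 0 means vaccination #1 throughout, that the 30-day window in 9.10 applies to steroids as well as to other drugs, and that the 30-day duration in 10.6 governs steroids, so a shorter course is not caught by that section's general terms. Only the 14- to 29-day group depends on the third.

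Item 12 of 9.10 also keeps a Year 1 anchor for recent vaccines. That is not part of this point, because 10.6 restricts live and killed vaccines both before and after each vaccination.

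**What to change.** In 9.10 item 11, replace Study Day 0 with scheduled vaccine dose #4, matching 9.6 item 4. The look-back would then cover nominal Days 362 to 392 (main) and 418 to 448 (pilot), and would move with the actual dose date. The 14-day steroid threshold would apply to that window, which also covers the course still running at dose 4.

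The cost is a few words in one bullet, with the IRB and ethics committee approval that any protocol revision needs. No new visit, test or data item is required: 11.1.1 already elicits medical history and medication use at Year 2 screening, and Appendix A schedules medication review at the Year 2 visits. No other change is asked for.

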### **9.11 Exclusion Criteria for Group 4 (Year 2)**

An individual will be excluded from participating in this trial if any one of the following criteria is fulfilled:

1. Behavioral, cognitive, or psychiatric disease that in the opinion of the investigator affects the ability of the subject to understand and comply with the study protocol at a level appropriate for the subject's age.
2. Evidence of clinically significant neurologic, cardiac, pulmonary, hepatic, endocrine, rheumatologic, autoimmune, hematological, oncologic, or renal disease by history, physical examination, and/or laboratory studies including urinalysis.
3. History of adverse reactions to artemether/lumefantrine in the past
4. History of receiving any investigational product within the past 30 days.
5. Current or planned participation in an investigational vaccine study until the last required protocol visit.
6. Receipt of:
  - Investigational malaria vaccine in the last 2 years.
7. Any other condition that in the opinion of the investigator would jeopardize the safety or rights of a subject participating in the trial, interfere with the evaluation of the study objectives, or would render the subject unable to comply with the protocol.

## **9.12 Justification for Exclusion of Special Populations**

### **9.12.1 Justification of Exclusion of Pregnant Women**

This study will not vaccinate pregnant women during the course of the study; they will be excluded from this cohort. The effects of Pfs230D1M-EPA/AS01 on the developing human fetus are unknown with the potential for teratogenic or abortifacient effects. In a reproductive and developmental toxicity study in female rats who were administered SHINGRIX or the AS01B adjuvant alone, no adverse effects on preweaning development up to post-natal day 25 were observed, and there were no vaccine-related fetal malformations or variations.

In addition, hepatitis A vaccine (HAVRIX) and typhoid vaccine (TYPHIM Vi) and meningococcal vaccine (Menactra) are classified as FDA pregnancy risk category C. Though, according to the Advisory Committee on Immunization Practices (ACIP), administration of inactivated virus vaccines to pregnant women have not resulted in adverse effects in the fetus. The ACIP recommends vaccination during pregnancy when the likelihood of disease exposure is high, potential infection would cause harm to mother or fetus, and when the vaccine is unlikely to cause harm. The manufacturer recommends administration of the vaccine to pregnant women only if clearly needed.

### **9.12.2 Justification for Exclusion of Children Under the Age of Five (Vaccination)**

Children under the age of 5 years are excluded from this study because there are insufficient data regarding dosing or AEs available in adults to judge the potential risk in children in this age group. Some evidence suggests an increased risk of febrile seizures with receipt of AS01 from RTS,S/AS01 studies in young children; since febrile seizures in the general population are most likely to occur in children under the age of 5 years, children under 5 years of age are excluded from vaccination. In addition, Malian children under 5 years of age receive monthly antimalarial treatments with long acting agents (termed Seasonal Malaria Chemoprevention), which limits their rates of parasitemia and especially gametocytemia, and as a consequence these children are not a primary target for transmission blocking vaccine assessment.

## **10 Study Agents**

### **10.1 Pfs230D1M-EPA/AS01**

#### **10.1.1 Manufacturing**

PpPfs230D1M and EcEPA lots, both manufactured at the Walter Reed Bioproduction facility (Silver Spring, Maryland) in current Good Manufacturing Practices (cGMP) compliance, were used to manufacture the conjugate. PpPfs230D1M is a *Pichia*-expressed recombinant subsegment (S542-G736) of Pfs230 with a molecular mass of 21,854 Daltons. EcEPA is an *Escherichia coli*-expressed recombinant protein with a molecular mass of 66,975 Daltons. The Pfs230D1M-EPA conjugate was produced by reaction between thiolated PpPfs230D1M and

maleimide-activated EcEPA, followed by purification using size-exclusion chromatography. The Pfs230D1M-EPA conjugate was manufactured at Walter Reed Bioproduction facility in cGMP compliance in May 2015 and July 2016.

The Pfs230D1M-EPA was formulated as conjugated Pfs230D1M in 4 mM phosphate-buffered saline (PBS) to a 2X dilution of the high dose (160 µg/mL in 0.5 mL volume) in cGMP compliance at Walter Reed Bioproduction facility in April 2016 or at the Biopharmaceutical Development Program (BDP) in December 2018 and is provided as a single use vial. AS01B adjuvant was manufactured for use in the SHINGRIX vaccine by GSK as 100 µg/mL MPL and 100 µg/mL QS21 in a liposomal formulation in a volume of 0.625 mL. For each dose of vaccine, the two single-use vials, one of Conjugated Pfs230D1M in 4mM PBS, and one of AS01B, will be mixed 1:1 at bedside. The vaccine will be mixed and drawn up into the syringes directly prior to injection. A final dose of 0.5 mL will administer 40 µg conjugated Pfs230D1M, 31 µg or 36 µg conjugated EPA in AS01 (25 µg MPL+ 25 µg QS21 liposomal formulation).

### **10.1.2 Disposition and Dispensation**

The Pfs230D1M-EPA vials will be supplied to the study site pharmacist by the Sponsor or Sponsor Representative. The Sponsor receives the product from Pilot Bioproduction Facility, Walter Reed Army Institute of Research, Silver Spring, Maryland, where the materials were formulated and packaged, or from ThermoFisher BioServices in Gaithersburg, MD where additional product manufactured at BDP is stored. The AS01B vials will be purchased as manufactured for the SHINGRIX vaccine by GSK.

